### Appendices

#### Appendix A Study Procedure Calendar

## 1.0 Background

### Parenteral Nutrition Associated Liver Disease (PNALD)

Parenteral nutrition (PN) provides intravenous nutritional supplementation for patients unable to absorb adequate enteral nutrients secondary to insufficient intestinal length or function. PN contains the macronutrient building blocks of the human diet in their most elemental forms (amino acids and dextrose) and is commonly administered with a fat emulsion to avoid essential fatty acid deficiency and to provide a calorically dense source of non-protein calories. In addition, PN contains the essential micronutrients (electrolytes, trace elements, and vitamins) to provide an optimal nutritional regimen. Before the development of PN in the late 1960's, patients with insufficient gastrointestinal absorptive function commonly died of starvation and subsequent complications of malnutrition(1, 2). Today, more than 30,000 patients are permanently dependent on parenteral nutrition for survival. However, PN continues to be associated with hepatic injury that occurs at an unpredictable rate and includes both biochemical, i.e., elevated serum bilirubin, aminotransferase and alkaline phosphatase, and histologic alterations such as steatosis, steatohepatitis, lipidosis, cholestasis, fibrosis, and cirrhosis (3, 4). These abnormalities, which worsen with the duration of PN administration, are more prevalent in the pediatric population. Additional risk factors for this condition include prematurity, low birth weight, long-term use of PN, the lack of concomitant enteral intake, sepsis, and multiple operative procedures (5).

Although the pathological features of PNALD have been well described, the etiology, prevention, and treatment of this complication are not well understood. Multiple hypotheses exist to explain the pathogenesis of PNALD including altered gut hormonal profiles (6), the propensity for bacterial translocation in the absence of enteral intake (7, 8), intestinal stasis resulting in the reduced clearance of hepatotoxic bile acids (8), and direct deficiencies or toxic components of the PN solution itself resulting in excessive glucose calorie uptake, excessive lipid infusion, or nutritional deficiencies such as essential fatty acid deficiency (9-11). None of these theories has been confirmed consistently. The etiology of PNALD is currently considered multifactorial. Available treatment options for this disease process are limited and have achieved moderate success at best. Care of the PN-dependent patient is focused on gradually increasing enteral caloric intake as the residual bowel adapts allowing PN to be discontinued (12). In fact, it has been shown both experimentally and clinically that partial enteral nutrition, when tolerated, helps to protect against the development of PNALD (13-15). In severe cases of refractory hepatic failure, liver transplantation with or without accompanying small bowel transplantation remains the only treatment option.

### Role of Intravenous Fat Emulsion on PN Associated Liver Disease

Recent evidence demonstrates that lipids are metabolized differently depending on their route of administration. Enteral lipids are absorbed by the enterocyte in the small bowel mucosa in the form of a micelle and packaged into chylomicrons which are released into the portal venous system for ultimate uptake and disposal in the liver. Once in the bloodstream, these particles rapidly acquire apolipoproteins from circulating high-density lipoproteins and can subsequently be metabolized by the liver. The emulsified particles of commercially made and intravenously administered lipid emulsions, such as Intralipid®, mimic the size and structure of chylomicrons, but differ in their content. In contrast to chylomicrons, artificial lipid particles primarily contain essential fatty acids and omega-6 triglycerides and are devoid of cholesterol or protein. Recent studies suggest that these omega-6 fatty acid-containing emulsions are dependent on lipoprotein lipase, apolipoprotein E, and low-density lipoprotein receptors for clearance, and are metabolized with less lipolysis and release of essential fatty acids than are chylomicrons. In fact, it appears that they may be cleared as whole particles by tissues other than the liver.(16) These factors may account for the increased incidence of steatohepatitis associated with the intravenous administration of Intralipid®.

The mechanism of clearance of omega-3 fatty acid containing lipid emulsions is unknown, but appears to be largely independent of the pathways identified above (17). Furthermore, omega-3 fatty acid solutions have been shown to decrease de novo lipogenesis (18), prevent or attenuate PN-induced hepatosteatosis in rats (19) and guinea pigs and ameliorate the severity of high-fat diet-induced hepatosteatosis in rats (20). In addition, omega-3 fatty acids can interfere with the arachidonic acid

pathway of inflammation (18, 21). They can displace arachidonic acid from tissue fatty acid pools, thereby reducing the availability for eicosanoid-synthesizing enzymes and inflammation (21).

Table 1 summarizes the composition of Intralipid® and Omegaven™ fat emulsions.

Table 1

Comparison of Parenteral Fat Emulsions (10 grams fat/100 mL)

OIL	Intralipid®	Liposyn® II	Omegaven™
Soybean	10	5	
Safflower		5	
Fish			10
% FATS			
Linoleic	50	65	0.1-0.7
α-linolenic	9	4	<0.2
E.P.A.			1.3-2.8
D.H.A.			1.4-3.1
Arachidonic acid			0.1 -0.4
Glycerol	2.3	2.5	2.5
Egg Phospholipid	1.2	1.2	1.2
Available in the United States	Yes	Yes	No

## Rationale for Omegaven™ Treatment

Unlike conventional intravenous fat emulsions, Omegaven™ is comprised solely of fish oils containing primarily omega-3 fatty acids. Animal studies have shown that IV fat emulsions such as fish oil that are high in eicosapentaenoic and docosahexaenoic acid reduce impairment of bile flow as seen in cholestasis caused by conventional fat emulsions(19,20). We hypothesize that by administering Omegaven™ in place of conventional phytosterol/soybean fat emulsions, that the cholestasis may be reversed and patients will be able to be maintained on adequate PN until they are able to ingest adequate nutrition enterally.

## 2.0 Rationale and Specific Aims

In the United States, patients dependent upon parenteral nutrition (PN) receive parenteral fat emulsions composed of soybean oils. Lipids are necessary in PN dependent patients due to their high caloric value and essential fatty acid content. They have been implicated in predisposing patients to PN associated liver disease. Phytosterols such as those contained in soybean oils are thought to have a deleterious effect on biliary secretion. Accumulation of lipids in the hepatic Kupffer cells may further impair liver function.

Children requiring prolonged courses of PN are at risk for developing PN associated liver disease. We hypothesize that although omega-6 fatty acid emulsions prevent fatty acid deficiency, they are not cleared in a manner similar to enteral chylomicrons and therefore accumulate in the liver and resulting in

steatotic liver injury. We further hypothesize that a fat emulsion comprised of omega-3 fatty acids (i.e., fish oil) such as Omegaven™ would be beneficial in the management of steatotic liver injury by its inhibition of *de novo* lipogenesis, the reduction of arachidonic acid-derived inflammatory mediators, prevention of essential fatty acid deficiency through the presence of small amounts of arachidonic acid, and improved clearance of lipids from the serum. Animal studies have shown that IV fat emulsions (IFE) such as fish oil that are high in eicosapentaenoic and docosahexaenoic acid reduce impairment of bile flow which is seen in cholestasis caused by conventional fat emulsions. Furthermore, we hypothesize that intravenous omega three fatty acids will be well tolerated and might reduce the inflammatory effect in the liver of prolonged PN exposure and could potentially reverse any hepatic dysfunction due to PN/IFE use. By administering Omegaven™ in place of conventional phytosterol/soybean fat emulsions we may reverse or prevent the progression of PN associated cholestasis and thus allow the patient to be maintained on adequate PN until they are able to ingest adequate nutrition enterally.

Assessment of the effect of treatment will be based on a non-randomized, open-labeled, prospective study of intravenously administered Omegaven™ fat emulsion to determine safety and preliminary efficacy in the treatment of PN associated liver injury.

### **Specific Aims /Objectives**

1. To determine the safety profile of an intravenous omega-3 fat emulsion (Omegaven™)

#### Hypothesis for Aim 1:

1.1 – PN containing Omegaven™ will be safe for patients with respect to the risk of unexpected bleeding, coagulopathies, and other adverse events.

1.2 – PN containing Omegaven™ will promote more short-term growth and development than conventional fat emulsions.

1.3-Incidence of sepsis will be similar to historical incidence of sepsis on TPN and IL™

2. To determine if established PN associated liver disease can be reversed or its progression halted by using a parenteral fat emulsion prepared from fish oil as measured by normalization of serum levels of hepatic enzymes and bilirubin.

#### Hypothesis for Aim 2:

2.1 – Our primary hypothesis is that, after reaching bilirubin levels  $> 2.5$  mg/dL, patients receiving Omegaven™ will reach a bilirubin level  $\leq 2$  mg/dL faster than patients receiving conventional fat emulsions. Additionally, patients receiving Omegaven™ will experience a decrease in their levels of bilirubin and other hepatic enzymes over time.

2.2 – Patients with surgical gastrointestinal disease and cholestasis will improve clinical hepatic status.

2.3 – Since patients receiving Omegaven™ will have improved immune function, they will have a lower infection rate than patients receiving conventional fat emulsions.

2.4 – Due to a better general hepatic condition, patients receiving Omegaven™ will also experience lower occurrence of liver transplant, death from hepatic associated causes, and blood transfusions.

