
In a second set of experiments, the same murine model was used to determine whether Omegaven™ (Fresenius- Kabi, Bad Homburg, Germany), a commercial fish oil fat emulsion available in Europe, would prevent fatty liver changes by enteral or parenteral routes of administration, and to determine the serum fatty acid profile of these animals. Animals receiving Omegaven™ via the oral and intravenous routes had completely normal livers on histology and MRI spectroscopy revealed normal liver fat content. Liver functions tests in orally treated animals were also within the norm, while there were minimal elevations in intravenously treated groups. There was no fatty acid deficiency in these groups as determined by Mead acid (5,8,11-Eicosatrienoic acid) levels in the serum fatty acid analysis. Mead acid is the only polyunsaturated fatty acid of note produced *de novo* by animals and only accumulates under the conditions of essential fatty acid deficiency. Furthermore, arachidonic acid levels were low in Omegaven™ treated animals consistent with previous reports. In a third set of experiments, mice were made severely fatty acid deficient. These mice were treated for 10 days with Omegaven™ and had complete reversal of their fatty acid deficiency.

Similarly, other investigators studied livers in a newborn pig model and showed that intravenous administration of fish oil, which consists primarily of omega-3 fatty acids, reduced parenteral nutrition-induced cholestasis.(22) However, the study was only 3 weeks in duration and long-term effects from administration of omega-3 fatty acids alone were not evaluated. In fact, the idea that one could remove an essential fatty acid from the standard regime of nutritional support by PN has not been accepted. It has

been thought that reduction of an essential fatty acid, such as omega-6, during long-term therapy would result in fatty acid deficiency and deterioration of the health of the patient. Our experience to date, as discussed below, demonstrates that the use of Omegaven™ as monotherapy does not result in the development of essential fatty acid deficiency and it can actually be used to as monotherapy to treat this deficiency state.

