## 4.0 Inclusion/Exclusion Criteria

### Inclusion Criteria:

1. Patients aged 0 to 2 years will be PN dependent (unable to meet nutritional needs solely by enteral nutrition) and are expected to require PN for at least another 30 days
2. Patients considered eligible for study participation must have parenteral nutrition associated liver disease (PNALD) as defined as a direct bilirubin of >2.5 mg/dl or more. Other causes of liver disease should be excluded. A liver biopsy is not necessary for treatment.
3. Signed patient informed consent.

4. The patient must have utilized standard therapies to prevent the progression of his/her liver disease including surgical treatment, cyclic PN, avoiding overfeeding, reduction/removal of copper and manganese from PN, advancement of enteral feeding, and the use of ursodiol (i.e., Actigall®).

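### Primary hypothesis 2.1 claims faster normalisation than on conventional emulsions, but the visible plan names a soybean group without defining it and states the primary event two ways

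*Combined protocol and SAP*

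**What the plan says.** **Claim.** Section 2.0, item 2.1, is labelled the primary hypothesis. It predicts that, once bilirubin has exceeded 2.5 mg/dL, Omegaven infants reach 2 mg/dL or less "faster than patients receiving conventional fat emulsions".

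**Other claims against the same comparator.** Item 1.2 expects that Omegaven "will promote more short-term growth and development than conventional fat emulsions". Item 2.3 expects that "they will have a lower infection rate than patients receiving conventional fat emulsions". Item 2.4, without naming the comparator, says that Omegaven patients "will also experience lower occurrence of liver transplant, death from hepatic associated causes, and blood transfusions". Item 1.3 has a historical reference, for sepsis only and without a source: "Incidence of sepsis will be similar to historical incidence of sepsis on TPN and IL™".

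**Who is enrolled.** Sections 2.0 and 5.0 describe an open-label, prospective study of Omegaven without randomisation, aimed at safety and preliminary efficacy. Section 4.0 admits infants with liver disease "as defined as a direct bilirubin of >2.5 mg/dl or more" who are "expected to require PN for at least another 30 days". Section 6.0 starts Omegaven after baseline laboratory tests and describes no other lipid assignment.

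**Analysis.** Section 10.0 lists direct bilirubin among outcomes measured in the Omegaven group. It lists a further set of safety outcomes for Omegaven and soybean groups, and refers to both groups in the trend models. Its primary efficacy outcome runs from baseline to the first of three consecutive bilirubin values below 2 mg/dL. Primary safety analyses are descriptive.

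**The concern.** A claim that one group normalises faster than another needs two defined sets of patients, a common start of the clock and a common event. For the soybean side, the visible text gives no source, calendar period, eligibility, time zero or follow-up. If such a series is assembled later, those choices would be made by people who already know how the open-label Omegaven infants fared; Section 7.0 reports 13 infants in the study when it was written. Each choice can move the result, and none would be fixed in advance.

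The primary event is also worded differently in the hypothesis and in the analysis section, so two analysts could date normalisation differently in the same infant.

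**Working it through.** **1. Can anything in the visible text supply the comparison?**

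| Candidate | Where | Can it give a soybean time to normalisation? |
|---|---|---|
| Concurrent control arm | Sections 2.0, 4.0, 5.0, 6.0 | No such arm is described |
| Soybean group | 10.0, safety | Named but not defined; bilirubin is not among its listed outcomes |
| Second group in trend models | 10.0, efficacy | Named but not defined |
| Before/after comparison | 10.0, safety | No. It covers safety and tolerability only, and infants enter with direct bilirubin above 2.5 mg/dL, so the soybean period before entry is not a comparable time to normalisation |
| Historical reference | 2.0, item 1.3 | Sepsis only |
| Confounder adjustment | 10.0, efficacy | Stated only for the PELD score comparisons |

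**2. How far does the gap reach?** Seven hypotheses are listed: 1.1, 1.2, 1.3, 2.1, 2.2, 2.3 and 2.4. Items 1.2, 2.1 and 2.3 name the conventional-emulsion comparator and 2.4 implies it: 3 + 1 = 4 of 7. Counting 1.3, which also needs unsourced soybean data, makes 5 of 7.

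**3. Is the primary event the same in both places?**

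| Element | Item 2.1 | Section 10.0 |
|---|---|---|
| Threshold | ≤ 2 mg/dL | < 2 mg/dL |
| Confirmation | none stated | first of three consecutive values |
| Clock | after exceeding 2.5 mg/dL, which may set time zero or only describe the population | from baseline, not defined there; Section 6.0 suggests before Omegaven |
| Fraction | not named | not named in the primary sentence; following sentences say direct |

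Threshold and confirmation differ. The clock is ambiguous, and a soybean infant has no stated baseline under either reading.

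**4. Illustrations.** The plan's visible text gives no sample size, event count, power or alpha, so there is no figure to reproduce. The following use assumed inputs. They show why the choices matter and are not evidence of the defect.

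- *Clock.* Suppose soybean infants are counted from the 2.5 mg/dL crossing and Omegaven infants from first infusion d weeks later, if not yet normalised, with no drug effect. Assume Weibull times with shape k and a 12-week median: λ = 12/(ln 2)^(1/k), and the Omegaven median is λ[(d/λ)^k + ln 2]^(1/k) − d. With d = 4: 8.65 weeks for k = 2 (28% shorter), 12.0 for k = 1, 16.67 for k = 0.7 (39% longer). With d = 1: 11.04 (8% shorter), 12.0 and 14.12 (18% longer). With d = 0 there is no bias.
- *Event.* Assume weekly values, a start of 6 mg/dL, a 4-week half-life and log-normal variation. A first single value ≤ 2 and the first of three consecutive values < 2 fall in different weeks in 4.4%, 25.5% and 44.6% of simulated infants at SD 0.1, 0.2 and 0.3.
- *Starting level.* Under a common exponential decline, ln(6/2)/ln(3/2) = 2.71: a start of 6 mg/dL takes 2.7 times as long to reach 2 as a start of 3.
- *Precision.* Thirteen is a count to date, not a planned size. If 9 of 13 normalised, the exact 95% interval would be 39% to 91%. With 9 events per group and a true hazard ratio of 1, SE = √(1/9 + 1/9) = 0.471, giving an expected interval of 0.40 to 2.52.

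**The case against.** **Parts of the document are not visible.** The Study Schema listed in the contents, the opening pages and some text between the infant data in Section 3.0 and Section 4.0 cannot be read. Section 3.0 also points forward: "Our experience to date, as discussed below, demonstrates". That text may describe other patients, and a comparator could be defined there. This stands, and limits the point to the visible text. It does not touch the event mismatch, which lies between two visible sections.

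**The efficacy comparison sentence breaks off.** The sentence in Section 10.0 that begins to describe crude comparisons of time to normalisation names no comparator. This may be damage in the copy, so nothing here rests on it.

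**The fraction.** A reader might infer that 2.1 and Section 10.0 use different bilirubin fractions. The documents do not support that. Neither primary sentence names one. Eligibility uses direct bilirubin with the same 2.5 mg/dL threshold, Section 10.0 goes on to speak of direct bilirubin, and total bilirubin of 1.2 is a separate outcome. The fraction is unnamed, with direct implied.

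**The plan is already modest.** Efficacy is called preliminary, and primary safety analyses are descriptive with significance testing secondary. So the two-group safety outcomes need no relabelling. But 2.1 is still called primary and still claims a difference between groups.

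**A hypothesis need not carry a confirmation rule.** That is fair, and the event illustration comes from reading 2.1 as a single unconfirmed value. The strict and non-strict thresholds still have to be reconciled.

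**Conclusion.** The concern holds, limited to the visible text. The primary hypothesis compares groups, the visible plan enrols and treats only Omegaven infants, and the soybean group is named but not defined. The primary event is stated two ways. Followed as written, the plan cannot test 2.1 without choosing patients, clock and event after open-label results exist. This should be corrected before any comparative efficacy conclusion is drawn.

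The scope is four of seven hypotheses, or five with the sepsis reference. The size of any bias cannot be derived from the documents.

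A reader might go further and infer that no comparator is defined anywhere, or that the study cannot address Aim 2. Neither follows. Unseen pages could hold a definition, and whether established liver disease reverses can be described in one arm. An external soybean series is also a usable source of preliminary evidence if specified in advance. Confidence is medium because of the unseen pages.

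**What to change.** **Primary objective.** Restate 2.1 as a single-arm estimate in Omegaven infants, for example the cumulative incidence of normalisation, with median time and 95% confidence interval. Count from first Omegaven infusion to the first of three consecutive direct bilirubin values below 2 mg/dL. Use identical wording in 2.1 and Section 10.0.

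**Death and transplant.** Treat both as competing events. Section 10.0's analysis excluding these infants can remain as a sensitivity analysis. Its worst-outcome rule belongs to the trend models and does not settle the time-to-event outcome.

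**Disclosure.** State that the clarified clock and fraction were fixed after 13 infants had been treated open-label. The three-value event is already in Section 10.0, and the visible text does not date it relative to those infants.

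**Soybean comparisons.** Label those behind 1.2, 2.1, 2.3 and 2.4 exploratory, and keep the two-group safety outcomes descriptive. If a bilirubin comparison is retained, fix before looking at data:

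- source, period and eligibility, with a chart rule for the prospective judgement of further PN need in Section 4.0;
- a common time zero, with the wait before Omegaven handled by delayed entry or time-varying treatment;
- adjustment for direct bilirubin at time zero.

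**Cost.** Wording changes in the protocol and analysis section, and a more modest efficacy claim. Chart review of soybean infants is needed only if the comparison is kept.

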## **3.0 Animal Studies and Previous Human Studies**

### **Animal Studies**

In initial studies at Children's Hospital Boston, they hypothesized that the development of PNALD may be dependent on both the route and quantity of fat administration and that omega-3 fatty acids would prevent or reduce *de novo* lipogenesis and the subsequent liver injury independent of the route of administration. Specifically, they characterized a previously established murine model of PN-associated liver injury to investigate whether enteral lipid administration would protect against the development of steatohepatitis in PN-dependent animals. This murine model of enteral PN-induced steatohepatitis is largely due to a high carbohydrate load and essential fatty acid deficiency. Although this model is not

replicative of the clinical setting, it is a model that maximizes liver steatosis. In this model, mice are treated with oral PN for 19 days before being sacrificed. These animals develop severe fatty liver changes demonstrated by MRI spectroscopy and histology (H&E, PAS, and oil red O staining), and also have biochemical changes consistent with liver injury (elevated alkaline phosphatase and serum transaminases). Experimental groups were supplemented with Intralipid® by several routes of administration including orally, intravenously, and subcutaneously. Other groups were also supplemented with omega-3 fatty acids (Omegaven™) by the same routes of administration. In this study they found a consistent pattern of protection against PN-associated steatohepatitis by administering enteral Intralipid® (22). In mice that received the highest dose of enteral Intralipid®, there was a marked decrease in the extent of overall liver injury as measured by gross inspection, histologic analysis, liver fat content, and serum liver enzyme levels. In all areas of this investigation, mice treated with enteral lipid most closely resembled the control mice that did not receive PN as part of the experimental protocol. These results were in complete contrast to the extensive fatty infiltration and evidence of hepatic injury found in mice that received PN without lipid supplementation as well as in mice that received PN with intravenous Intralipid®. Mice receiving intravenous Intralipid® had the most severe liver changes. Both groups of animals developed marked hepatic steatosis with macrovesicular fatty infiltration and significant elevations in spectroscopic liver fat content and serum transaminase levels. In addition, the effect of enteral Intralipid® supplementation appeared to be dose-dependent; mice receiving one-third the dose of enteral Intralipid® showed improved liver histology but still demonstrated a moderate degree of liver injury by spectroscopy and serum liver function tests. The nutritional model employed in this study provided all experimental mice with enteral PN solution *ad libitum*. In this way, mice were not force-fed PN and self-regulated their PN intake by demands for growth and energy. Importantly, all mice gained weight throughout the 19-day protocol, and there were no differences in weight gain parameters between the groups. The PN solution was a typical pediatric stock formula mixed at their institution containing 20% dextrose and 2% amino acids. Each milliliter of this formula provides 0.2 g (0.68 kilocalories) of dextrose and 0.02 g (0.08 kilocalories) amino acid. As the daily intake per animal of PN averaged 15 ml, mice were ingesting approximately 11.4 kilocalories/day and 456 kilocalories/kg/day. This caloric load is similar to the established dietary energy needs of the mouse (23). The parenteral fat source used in this study was Intralipid® 20% (Baxter, Deerfield, Illinois), which is a soybean oil-based emulsion. Each milliliter of this emulsion contains 0.2 g (2.0 kcal) of fat. They recognized that the model may not completely match the clinical, human, setting of intravenous PN-administration; however, their goal was to produce a fatty liver with biochemical evidence of injury.

In a second set of experiments, the same murine model was used to determine whether Omegaven™ (Fresenius- Kabi, Bad Homburg, Germany), a commercial fish oil fat emulsion available in Europe, would prevent fatty liver changes by enteral or parenteral routes of administration, and to determine the serum fatty acid profile of these animals. Animals receiving Omegaven™ via the oral and intravenous routes had completely normal livers on histology and MRI spectroscopy revealed normal liver fat content. Liver functions tests in orally treated animals were also within the norm, while there were minimal elevations in intravenously treated groups. There was no fatty acid deficiency in these groups as determined by Mead acid (5,8,11-Eicosatrienoic acid) levels in the serum fatty acid analysis. Mead acid is the only polyunsaturated fatty acid of note produced *de novo* by animals and only accumulates under the conditions of essential fatty acid deficiency. Furthermore, arachidonic acid levels were low in Omegaven™ treated animals consistent with previous reports. In a third set of experiments, mice were made severely fatty acid deficient. These mice were treated for 10 days with Omegaven™ and had complete reversal of their fatty acid deficiency.

Similarly, other investigators studied livers in a newborn pig model and showed that intravenous administration of fish oil, which consists primarily of omega-3 fatty acids, reduced parenteral nutrition-induced cholestasis.(22) However, the study was only 3 weeks in duration and long-term effects from administration of omega-3 fatty acids alone were not evaluated. In fact, the idea that one could remove an essential fatty acid from the standard regime of nutritional support by PN has not been accepted. It has

been thought that reduction of an essential fatty acid, such as omega-6, during long-term therapy would result in fatty acid deficiency and deterioration of the health of the patient. Our experience to date, as discussed below, demonstrates that the use of Omegaven™ as monotherapy does not result in the development of essential fatty acid deficiency and it can actually be used to as monotherapy to treat this deficiency state.

